Additional analyses may be performed for the primary efficacy variable adjusting for Baseline covariates in addition to Baseline Hurley Stage, if necessary. Results from any additional analyses will not be used as a substitute for the planned analyses, but may be used as supplemental information for the study report.

D. Primary Efficacy Endpoint Analysis

Primary Analysis

The primary efficacy objective is to evaluate the efficacy of avacopan compared to placebo in subjects with Hurley Stage II or III HS based on subjects achieving a Hidradenitis Suppurativa Clinical Response (HiSCR) after 12 weeks of treatment. To address this objective, the following hypotheses will be tested using the data collected from Period 1 after the last subject has completed Period 1:

- The null hypothesis (H₀) is that the avacopan group is not different from the placebo control group when comparing the HiSCR rate at Week 12.
- The alternative hypothesis (H₁) is that the avacopan group is different from the placebo control group when comparing the HiSCR rate at Week 12.

To address the multiplicity issue with two dose groups, a fixed hierarchical testing procedure will be used for the comparisons of the Avacopan 10 mg vs. Placebo and Avacopan 30 mg vs. Placebo to maintain the overall Type I error at 0.05. The hypothesis testing will test the Avacopan 30 mg vs. Placebo first: if the p-value is \leq 0.05, then 10 mg Avacopan vs. Placebo will be tested at the α = 0.05 level. If the test of Avacopan 30 mg vs. Placebo is not significant at the α = 0.05 level, the 10 mg Avacopan vs. Placebo will be tested as an exploratory analysis.

To compare treatment groups, the proportion of subjects achieving HiSCR at Week 12 will be tested using the Cochran-Mantel-Haenszel (CMH) test, stratified by Hurley Stage (Stage II vs. III), concomitant antibiotic therapy with allowed antibiotics (Yes vs. No) and prior anti-TNF drug use (Treatment naïve vs. Previous treatment). The two-sided 95% confidence intervals for the difference in proportions (avacopan minus placebo control) will be calculated using the stratified Newcombe hybrid-score method. If the sample becomes sparse in one of the strata, the stratification factor will be removed from the stratified analysis.

The primary efficacy analysis will be carried out in the ITT1 Population. In addition, the primary efficacy endpoint will be analyzed in the PP1 Population.

The following provides sample code for implementing the CMH analysis for 30 mg avacopan vs. placebo:

```
ods output commonpdiff=pdiff1;
proc freq data=test(where=(trt in (0, 2)));
```

where

- HS is the variable for Hurley Stage (Stage II vs. III)
- ANTIB is the variable for allowed antibiotics (Yes vs. No)
- ANTITNF anti-TNF drug use (Treatment naive vs. Previous treatment)
- TRT is the variable for treatment (0 for placebo; 1 for avacopan 10 mg; 2 for avacopan 30 mg)
- RESP is the response variable for achieving HiSCR at Week 12 (0 for No, 1 for Yes).

Missing assessments were handled with the use of NRI as the primary approach to handling missing data.

Sensitivity Analyses

Several sensitivity analyses will be conducted on the primary efficacy endpoint in the ITT1 Population. Each are described below:

1) Imputation of Missing Values with Multiple Imputation (MI) Analysis

The Multiple Imputation analysis will be carried out in three steps;

- Imputation of missing data. The imputation will be generated for the three components of HiSCR (abscess, draining fistula, inflammatory nodule counts). The variables to be included in the imputation model are: Baseline Hurley Stage, Baseline antibiotic therapy, Baseline anti-TNF-α treatment, treatment group, and values at each visit from Baseline up to Week 12. For each HiSCR component, 100 'complete' data sets will be generated using SAS PROC MI utilizing the MCMC algorithm. The seeds for the imputation will be specified as the value "12061", "36102", and "94218" for imputation of abscess, draining fistula, and inflammatory nodule counts, respectively. The 'complete' data sets for the individual components of the HiSCR will be merged by imputation number to allow calculation of the HiSCR and creation of 100 'complete' data sets for evaluation of HiSCR. Subjects who received concomitant anti-TNF-α treatment or other treatments with clinically relevant impact on HS will be forced as non-responders for all of 100 'complete' data sets.
- Analysis of imputed data sets. A CMH test, stratified by Baseline Hurley Stage (II vs. III), Baseline antibiotic therapy (Yes vs. No), Baseline anti-TNF-α treatment (Treatment naïve vs. Previous treatment) will be used to analyze each 'complete' HiSCR data set.

Synthesis of imputation and analysis results. SAS PROC MIANALYZE
will be used to generate the final estimate of the proportion difference
between avacopan and placebo groups and the corresponding 95%
confidence interval.

2) Non-Responder Imputation for Any Add-on Antibiotics/Other Concomitant Medications Use

All subjects with any add-on antibiotics (any antibiotics other than the concomitant at Baseline) or with dose increase from baseline concomitant antibiotics prior to Week 12, regardless the reason for use; or other concomitant medications listed below will be imputed as non-responders:

- Add-on antibiotics
- Concomitant Anti-TNF-α treatment
- Concomitant other systemic treatment for HS. E.g., methotrexate, cyclosporine, retinoids, and fumaric acid esters, etc.

3) LOCF for HiSCR

Subgroup Analysis

Subgroup analyses will be performed for the primary efficacy endpoint in the ITT1 Population.

The subgroups are defined as follows:

- Randomization stratification variables
 - Hurley Stage (II, III)
 - Concomitant antibiotic therapy (Yes, No)
 - Anti-TNF-α treatment (Treatment naïve, Previous treatment)
- Sex (Male, Female)
- BMI category: Normal (< 25 kg/m²), Overweight (25 − < 30 kg/m²), obese (30 − < 40 kg/m²), Morbid obesity (≥ 40 kg/m²)
- Age at diagnosis of HS (< median, ≥ median)
- Age at study entry (<65 years vs. ≥ 65 years)
- Duration of HS (< median, ≥ median)
- Race (White vs. None-White)
- Baseline AN count (<5, 5-10, >10)
- Baseline inflammatory nodule count (< median, ≥ median)
- Baseline abscess count (< median, ≥ median)

- Baseline draining fistula count (< median, ≥ median)
- Baseline modified Sartorius score (< median, ≥ median)
- Previous systemic HS treatment (includes TNF inhibitor use but excludes antibiotic use)
- Geographic distribution (Northeastern Region, Southeastern Region, Western Region, Midwestern Region, and Southwestern Region)

These summaries will be based on imputed data (NRI for binary variables). If the sample becomes sparse in one of the subgroup strata, the subgroup variable will be collapsed or removed from the subgroup analysis.

Exploratory Analysis

The avacopan 10 mg vs. 30 mg groups will be tested for the primary efficacy endpoint if the primary efficacy endpoint tests of both avacopan 10 mg vs placebo and avacopan 30 mg groups vs placebo are statistically significant in the ITT1 Population.

E. Secondary and Other Efficacy Endpoints Analyses

The following missing data handling rules will apply:

Secondary/Other Efficacy Endpoints

- For binary efficacy variables, NRI imputation method will be used for missing data. For NRS30 in Period 1, multiple imputation method will be applied similarly as the primary endpoint.

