4.1. Inclusion Criteria

Subjects must meet all of the following inclusion criteria in order to enter the study:

1. Aged at least 18 years of age;
2. Clinical diagnosis of HS (Hurley Stage II or III), confirmed by a dermatologist, for at least 6 months prior to Screening. Hurley Stage II disease is defined as having one or more widely separated recurrent abscesses with tract formation and scars; Stage III disease is defined as having multiple interconnected tracts and abscesses across an entire anatomical area with diffuse or near diffuse involvement;
3. HS lesions are present in at least 2 distinct anatomic areas (e.g., left and right axilla; or left axilla and left inguino-crural fold), one of which is Hurley Stage II or Hurley Stage III;
4. Inadequate or loss of response to a systemic course of antibiotics of 90 days. However, a subject who has completed less than 90 days of antibiotic treatment may be allowed into the study upon discussion with the Medical Monitor if: 1) the subject has demonstrated intolerance to or contraindication for antibiotics to treat HS, or 2) it was determined by the Investigator that an antibiotic course of at least 28 days to treat HS did not benefit the subject and a continued antibiotic therapy would therefore not be indicated.

Inadequate or loss of response is defined if the following was observed despite antibiotic treatment:

- a. Progression of Hurley Stage (i.e., the Hurley Stage of at least one affected anatomic region progressed from I→II, II→III, or I→III);
 - b. Subject required at least one intervention (e.g., incision and drainage or intralesional injection of corticosteroid);
 - c. Subject experienced pain interfering with activities of daily living, with unsatisfactory relief from over-the-counter analgesics (e.g., ibuprofen or acetaminophen);
 - d. Subject experienced pain requiring opioids, including tramadol;
 - e. Subject experienced drainage interfering with activities of daily living (e.g., requires multiple dressing changes and/or changes of clothes daily);
 - f. Subject experienced an increase in the number of anatomic regions affected by HS;
 - g. Subject experienced at least one new abscess or one new draining fistula.
5. Must have at least 5 inflammatory nodules or abscesses at Screening;
 6. Must agree to use a topical antiseptic daily over the course of the study; topical antiseptics may include but are not limited to chlorhexidine, triclosan, benzoyl peroxide, or diluted bleach in bath water;

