4.2. Exclusion Criteria

Subjects will be excluded from study participation if any of the following criteria are met:

1. Pregnant or breast-feeding;
2. Any other skin disease that may interfere with the assessment of HS, such as a viral or fungal skin infection;
3. Rapidly progressive, expanding HS within 30 days prior to Screening;
4. More than 20 draining fistulae at Screening;
5. Any anti-TNF- α treatment for HS or for other conditions prior to Day 1 visit will be prohibited. Exception: subjects who were previously treated with an anti-TNF- α drug and discontinued treatment >12 weeks prior to Day 1 visit are allowed for enrollment;
6. Systemic antibiotics are generally excluded. Exception: subjects on systemic antibiotic treatment with doxycycline or minocycline who have been on a stable dose for at least 28 days prior to Day 1. After a pre-specified percentage of subjects on these permissible antibiotic treatments have been enrolled, no further enrollment of such subjects will be allowed;
7. Topical antibiotics use within 14 days prior to Day 1;
8. Have started a topical prescription medicine for HS within 14 days prior to Screening or is anticipated to start during the Screening period. Topical prescription medicine for HS other than topical antibiotics that was started >14 days prior to Screening is allowed;
9. With the exception of permissible antibiotic treatment regimens, have received a systemic medicine for HS or with a potential therapeutic impact on HS, including systemic antibiotic therapy, biologics and other systemic therapies such as methotrexate, cyclosporine, retinoids,

and fumaric acid esters, etc., within a minimum of 30 days or 5 half-lives (whichever is longer) after taking the last dose;

10. Have received within 14 days prior to the Day 1 visit, or is expected to require during the study, oral or transdermal opioid analgesics (except for tramadol) for any reason; non-opioid analgesics are allowed if the subject is on a stable dose for at least 14 days prior to the Day 1 visit (“as needed” dosing is not considered to be a stable dose);
11. Currently taking a strong inducer of the cytochrome P450 3A4 (CYP3A4) enzyme, such as carbamazepine, phenobarbital, phenytoin, rifampin, or St. John's wort;

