8.5.3. Other Efficacy Endpoints

The following efficacy endpoints will be analyzed from Day 1 to each timepoint up to Week 44, where applicable:

1. Proportion of subjects achieving HiSCR;
2. Proportion of subjects achieving at least 30% reduction and at least 1 unit reduction from Day 1 in subject's global assessment of skin pain (NRS30), in subjects with a Day 1 NRS of at least 3;
3. Proportion of subjects with baseline Hurley Stage II who achieved an abscess and inflammatory nodule count of 0, 1, or 2;
4. Change from Day 1 in inflammatory nodule count, abscess count, draining fistula count, and total AN count;
5. Change from Day 1 in the Sartorius score, modified Sartorius score, IHS4 score, and HS-PGA to quantify the severity change of HS;

6. Change from Day 1 in patient-reported outcomes: SF-36 v2, EQ-5D-5L, HiSQOL, and DLQI;
7. Proportion of subjects who experienced flare, defined as an at least 25% increase in AN counts with a minimum increase of 2 AN lesions relative to Day 1;
8. Duration of flare in days (calculated from the day when flare is observed to the day prior to the observation that flare is no longer present; of note, there could be multiple periods that flares are observed, in which case, the total days from the multiple periods will be used);
9. Proportion of subjects who experience at least 25% increase in draining fistula counts with a minimum increase of 2 draining fistula counts relative to Day 1;
10. During Period 2, Proportion of subjects with a loss of response (LOR), defined as loss of at least 50% of AN count improvement achieved from Day 1 to Week 12;
11. Time to LOR during Period 2;
12. Proportion of subjects who received oral antibiotic rescue therapy;
13. Proportion of subjects who start disallowed opioid pain therapy;
14. Proportion of subjects who undergo lesion intervention due to HS;
15. Number of lesion interventions due to HS;
16. Health-economic information:
 - a. WPAI:SHP: Change from Day 1 to each timepoint during Period 1 and Change from Week 12 to each timepoint during Period 2 and including the follow-up period;
 - b. Hospitalizations (cumulative): Number of Hospitalizations total and due to HS, Number of days hospitalized, Number of days missed from work;
 - c. Emergency or Urgent Care visits (cumulative): Number of visits total and due to HS, Number of days (or hours where applicable) missed from work;

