Subjects will be asked to take 3 capsules of study drug orally with water and preferably with food every morning, and 3 capsules with water and preferably with food in the evening approximately 12 hours after the morning dose, as instructed. Study drug will be taken for 36 weeks (252 days) continuously.

VI. General Analytical Considerations

A. Baseline and Study Day

Baseline

Baseline for analysis purposes is defined as the last assessment prior to treatment start date/time.

For Subject's Global Assessment of Skin Pain (Numerical Rating Scale, Skin Pain NRS), the average of the last 7 assessments prior to the date of first dose of study drug will be used as Baseline. If there are only 3 to 6 daily assessments available, the average of the available assessments will be used. If there are 2 or less assessments available, the subject's Baseline will be considered as missing.

Change from Baseline

Change from baseline is defined as the post baseline value minus the baseline value. Percent change from baseline is calculated as follows: Percent change = (Change from baseline / Baseline) * 100.

Reduction from Baseline

Reduction from baseline is defined as the baseline value minus the post baseline value. Percent reduction from baseline is calculated as follows: Percent reduction = (Reduction from baseline / Baseline) * 100.

Study Day

Study day for analysis purposes is defined as (date of event – treatment start date) (+ 1 if the event occurs after treatment start date).

B. Analysis Visit Window

All visits including scheduled, unscheduled and early termination visits will be assigned to analysis visits using analysis visit windows based on the actual date the assessment took place. The start day of the analysis window will be calculated as the midpoint between the scheduled assessment and previously scheduled assessment for that parameter. The end day of the analysis window will be calculated as the midpoint between the scheduled assessment and the next scheduled assessment for that parameter. Where multiple measurements for a particular parameter appear within an analysis window, the scheduled visit will be used. If no scheduled visit appears in the analysis window, the result closest to the target day will be used. If equidistant and both are unscheduled and/or early termination visits, the later result will be used for the summary measure.

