3	The longest distance between two relevant lesions, or size if only one lesion	The longest distance between two relevant lesions (or size of lesion if single) in each region
	< 5 cm, 2 points < 10 cm, 4 points > 10 cm, 8 points	< 5 cm = 1 point 5-10 cm = 3 points > 10 cm = 9 points
4	Are all lesions clearly separated by normal skin? In each region yes = 0; no = 6	Are all lesions clearly separated by normal skin? In each region yes = 0; no = 9

Other Efficacy Endpoints

The following efficacy endpoints will be analyzed from Baseline to each timepoint up to Week 44, where applicable:

 Change from Baseline in inflammatory nodule count, abscess count, draining fistula count, total AN count, and non-inflammatory nodule count, nondraining and total fistula count.

Change from Baseline = Post Baseline Count - Baseline Count

 % change from Baseline in inflammatory nodule count, abscess count, draining fistula count, total AN count, and non-inflammatory nodule count, nondraining and total fistula count among subjects who have at least one corresponding lesion at Day 1.

% Change from Baseline = 100*Change from Baseline/Baseline Count

Proportion of subjects achieving HiSCR, HiSCR₇₅, and HiSCR₉₀.
 Please see the description of the Primary Endpoint for details.

% Reduction from Baseline in AN Count
$$= 100 \times \frac{\text{(Baseline AN Count - Post Baseline AN Count)}}{\text{Baseline AN Count}}$$

The proportion of subjects achieving HiSCR at Post Baseline visits will be calculated as those subjects having % Reduction from Baseline in AN count \geq 50 and (Baseline Abscess Count — Post Baseline Abscess Count \geq 0) and (Baseline Draining Fistula Count —

Post Baseline Draining Fistula Count $) \ge 0$

at Post Baseline visits divided by the total number of subjects in each treatment group.

HiSCR₇₅ or HiSCR₉₀ denotes 75% reduction or 90% reduction for the HiSCR definition instead of 50% reduction with no increase in the number of abscesses or draining fistulas count.

4) Proportion of subjects achieving at least 30% reduction and at least 1 unit reduction from Baseline in the subject's global assessment of skin pain (NRS30), in subjects with a Baseline NRS of at least 3.

Please see the description of item 2) in Secondary Endpoints for details.

% Reduction from Baseline in NRS =
$$100 \times \frac{\text{Baseline NRS-Post Baseline NRS}}{\text{Baseline NRS}}$$

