The DLQI is calculated by adding the score of each question. The maximum score is 30, and the minimum score is 0. The higher the score, the more quality of life is impaired.

Meaning of DLQI Scores

0-1 = no effect at all on subject's life

2-5 = small effect on subject's life

6-10 = moderate effect on subject's life

11-20 = very large effect on subject's life

21-30 = extremely large effect on subject's life

Change from Baseline in Score = Post Baseline Score - Baseline Score

8) Proportion of subjects who experienced flare, defined by at least a 25% increase in AN counts with a minimum increase of 2 AN counts relative to Baseline

The AN count is the sum of all abscesses and inflammatory nodules counts across all regions.

% Increase in AN counts

$$= 100 \times \frac{\text{(AN Counts at Day x} - \text{AN Counts at Baseline)}}{\text{AN Count at Baseline}}$$

The proportion of subjects who experienced flare at Post Baseline visits will be calculated as those subjects having % Increase in AN counts ≥ 25 and (Post Baseline AN Counts – Baseline AN Counts) ≥ 2 at Post Baseline visits divided by the total number of subjects in each treatment group.

9) Duration of flare in days (Observed case only)

> Duration of flare in days is calculated from the day when flare is observed to the day prior to the observation that flare is no longer present; of note, there could be multiple periods that flares are observed, in which case, the total days from the multiple periods will be used.

10) Proportion of subjects who experience at least 25% increase in draining fistula counts with a minimum increase of 2 draining fistula counts relative to Baseline.

% Increase in Draining Fistula Counts

The proportion of subjects who experienced at least 25% increase in draining fistula counts with a minimum increase of 2 draining fistula counts relative to Baseline at Post Baseline visits will be calculated as those subjects having % Increase in Draining Fistula Counts > 25 and

(Post Baseline Draining Fistula Counts —

Baseline Draining Fistula Counts) ≥ 2 at Post Baseline visits divided by the total number of subjects in each treatment group.

11) During Period 2, proportion of subjects with a loss of response, (LOR) defined as loss of at least 50% of AN count improvement achieved at Week 12 from Period 1.

AN in Period 2 – Week 12 AN $> \frac{1}{2}$ (Baseline AN – Week 12 AN)

i.e., AN in Period 2 > $\frac{1}{2}$ (Baseline AN +Week 12 AN)

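### The draining-fistula worsening endpoint (SAP VIII.B, Other Efficacy Endpoints, item 10) shows no rule for a baseline of zero; computed literally, a rise from 0 to 2 or more is not counted as worsening

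*SAP*

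**What the plan says.** SAP Section VIII.B, Other Efficacy Endpoints, item 10 names the endpoint as "Proportion of subjects who experience at least 25% increase in draining fistula counts with a minimum increase of 2 draining fistula counts relative to Baseline". Protocol Section 8.5.3, item 9 sets the same two conditions relative to Day 1.

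The calculation under item 10 takes the proportion "calculated as those subjects having % Increase in Draining Fistula Counts > 25 and" an absolute rise, with the sentence ending "Baseline Draining Fistula Counts) ≥ 2 at Post Baseline visits divided by the total number of subjects in each treatment group". Both conditions must hold, and the denominator is the whole group.

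The line that should show item 10's percent formula is not legible in the available text. Two other places indicate its form. SAP Section VI.A gives "Percent change = (Change from baseline / Baseline) * 100", and item 8 (flare) in the same list divides the rise in AN count by the baseline AN count.

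On entry, Protocol Section 4.1 states "Must have at least 5 inflammatory nodules or abscesses at Screening", and Section 4.2 excludes subjects with "More than 20 draining fistulae at Screening". There is an upper limit on draining fistulae but no lower one.

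For the percent-change summaries of lesion counts, SAP VIII.B restricts the analysis to a subset: "nondraining and total fistula count among subjects who have at least one corresponding lesion at Day 1". SAP Section III.A has the same restriction. None is visible for item 10.

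**The concern.** A percent-of-baseline criterion cannot be evaluated when the baseline is 0. The subjects concerned had no draining fistulae and then developed at least two, which is plainly worsening of the kind this endpoint is meant to record. If the undefined percentage is handled as a missing value, the comparison with 25 is false and the subject becomes a non-event without any flag.

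The SAP's general missing-data rule does not settle the case. Section VI.C treats a subject with missing data as not having responded. It does not say whether an undefined percentage counts as missing data, or what non-response means for an endpoint that measures worsening. Two competent programmers could report different rates from the same data at every visit to Week 44. The SAP tests comparisons of this kind at a two-sided 0.05 level.

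A smaller point sits in the same sentence. The endpoint is named with a threshold of at least 25%, but the calculation prints > 25.

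**Working it through.** The documents state no rate or power for this endpoint, so there is no figure of theirs to reproduce. The check applies the two conditions to each possible baseline.

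**Inputs**
- Percent increase = 100 × (post − baseline) / baseline (SAP VI.A; same form as item 8).
- Absolute rise of at least 2, and denominator = all subjects in the group (SAP VIII.B, item 10).
- Screening counts from 0 to 20 are eligible (Protocol 4.1 and 4.2).

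The SAP itself allows for subjects without draining fistulae. Its HS-PGA table has a Moderate category with 0 abscesses, 0 draining fistulae and 5 or more inflammatory nodules. The per-protocol criterion in Section VI.J needs only a positive total of scars and fistulae, so scars alone suffice.

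**Step 1: single cases**
- 1 to 3: 100 × 2/1 = 200%, rise 2: event.
- 0 to 2: 100 × 2/0, undefined, rise 2: not an event if computed literally.
- 0 to 5: 100 × 5/0, undefined, rise 5: the same.
- 0 to 1: rise 1, excluded by the minimum of 2, as is 1 to 2. This is by design and not a defect.

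**Step 2: smallest rise that counts, by baseline**

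| Baseline | Printed rule (> 25) | Named rule (≥ 25) |
|---|---|---|
| 0 | none | none |
| 1–7 | 2 | 2 |
| 8 | 3 | 2 |
| 9–11 | 3 | 3 |
| 12 | 4 | 3 |
| 13–15 | 4 | 4 |
| 16 | 5 | 4 |
| 17–19 | 5 | 5 |
| 20 | 6 | 5 |

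Baseline 0 is the only eligible value at which no rise of any size qualifies. The threshold sign matters only at 8, 12, 16 and 20 (8 to 10, 12 to 15, 16 to 20 and 20 to 25 are each exactly 25%).

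**Step 3: possible size**

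Let z be the share with baseline 0, q the proportion of these who gain at least 2, and w the event rate in the rest.
- Literal rule: (1 − z)w
- With zero baselines counted: zq + (1 − z)w
- Events missed per 130 subjects (the planned group size): 130zq

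The documents give none of z, q or w. Assumed for illustration: z = 20% to 60%, q = 5% to 20%, w = 15%.

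| z | Literal rule | Counted, q = 5% / 10% / 20% | Missed per 130 |
|---|---|---|---|
| 20% | 12% | 13% / 14% / 16% | 1.3 / 2.6 / 5.2 |
| 40% | 9% | 11% / 13% / 17% | 2.6 / 5.2 / 10.4 |
| 60% | 6% | 9% / 12% / 18% | 3.9 / 7.8 / 15.6 |

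For example, z = 40% and q = 10% give 0.40 × 0.10 + 0.60 × 0.15 = 0.13, and 130 × 0.04 = 5.2.

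**Step 4: difference between arms**

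With the same z in both arms, the literal rule drops the term z(q_avacopan − q_placebo) from the difference in proportions. If the two q values are equal, the difference does not change; otherwise the sign and size depend on quantities that the documents do not give.

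**The case against.** The strongest reply is that the SAP leaves the zero baseline unspecified and does not declare it a non-event. Item 10's formula line is not legible here, so a zero-baseline provision on that line cannot be ruled out. The outcome also depends on code: if the condition is programmed as post ≥ 1.25 × baseline, 0 to 2 passes. This stands as a limit on certainty. It does not remove the need for a rule, because the calculation sentence that can be read contains none.

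The printed > 25 may be a conversion artefact. Item 8 prints ≥ 25, item 10 says at least 25% in words, and the SAP schedule prints <4 weeks for screening where the SAP text has ≤ 4 weeks. This also stands, so the sign should be confirmed and not reported as an error.

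New draining fistulae do not go unseen in the trial. Any increase fails HiSCR, change in draining fistula count is a ranked secondary endpoint, and IHS4, also ranked, gives each draining tunnel a weight of 4. All three use counts or absolute differences. Item 10 is one of 17 other endpoints, and SAP Section VI.I calls comparisons of such endpoints supportive or exploratory, without multiplicity adjustment. This is correct and bounds the impact.

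A reader might go further and infer that no rise from zero, of any size, could ever be counted, or that event rates and the arm difference shrink in proportion to the share of zero-baseline subjects. The documents support neither. A rise from 0 to 1 is excluded by design, and non-counting of larger rises follows from a literal computation, not from a stated rule. Proportional shrinkage of the rates requires the same event rate in subjects with and without draining fistulae at baseline, for which there is no evidence; if zero-baseline subjects rarely gain two, the loss is close to nil.

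**Conclusion.** The point holds in a limited form. As legible, item 10 applies a percent-of-baseline condition in a population where a baseline of 0 is eligible, keeps those subjects in the denominator, and shows no rule for them. Computed literally, it classifies 0 to 2 or more as not worse while it classifies 1 to 3 as worse. The SAP made provision for the same problem in its percent-change summaries.

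This rests on two assumptions: that item 10's formula divides by baseline, as Section VI.A and item 8 do, and that an undefined percentage fails the comparison. The first is very likely; the second depends on programming.

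The size is unknown. The range of about 1 to 16 missed events per 130 subjects is illustrative only, and the effect on the arm difference could be nil or go in either direction. The primary endpoint and the ranked secondary endpoints are unaffected.

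**What to change.** Rewrite the calculation in SAP VIII.B, item 10 so that an event is:

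(post-baseline − baseline draining fistula count) ≥ 2 AND (baseline = 0 OR percent increase ≥ 25), divided by all subjects in the treatment group.

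This keeps the stated denominator and makes 0 to 2 or more an event, with 0 to 1 still a non-event. Check the source document for the threshold sign and make it ≥ 25, in line with the endpoint's name in both documents. State the formula in full.

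Restricting the denominator to subjects with at least one draining fistula at baseline, as in the percent-change summaries, would also remove the ambiguity. It would change the endpoint's population and leave new fistulae in zero-baseline subjects unreported, so the first option is preferable.

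The same clause could be added to the flare rule (item 8). It is optional there, because entry requires at least 5 nodules or abscesses at Screening and a zero AN baseline should be rare.

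The cost is one line of SAP text and one line of code, with no new data. It is best done before the unblinded Period 1 analysis; if done later, it should be labelled as a post hoc clarification.
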